112 document, with the ethical principles that have their origin in the Declaration of Helsinki, with  
113 the protocol described herein, and with the standards of Good Clinical Practice (GCP).

114 **Chapter 2: Study Enrollment and Baseline Data Collection**

115 **2.1 Participant Recruitment and Informed Consent**

116 Adults (age  $\geq 18$  years) with type 1 diabetes or type 2 diabetes using insulin therapy (Tidepool-  
117 compatible pump or injections) will be enrolled. Although the primary focus of the study is to  
118 enroll non-CGM users, CGM users whose glycemic control is suboptimal can be enrolled.  
119 Participation will be limited to U.S. residents in states where the virtual clinic is licensed; state  
120 eligibility will be verified as part of screening. Potential participants may be recruited through  
121 insurance providers, primary care networks, or health care providers. Potential participants also  
122 may become aware of the study by other means, such as another study participant.

123 Up to 800 individuals may sign the informed consent form to initiate screening. Enrollment will  
124 proceed with the goal of at least 300 participants initiating training for CGM use with the Virtual  
125 Clinic. The goal will be to limit T2D enrollment to no more than 100. Recruitment efforts will be  
126 focused on participants who receive diabetes care in a primary care setting rather than through an  
127 endocrinologist, with a goal of having at least 225 who have not seen an endocrinologist in the  
128 past six months. Eligible participants will be included without regard to gender, race, or  
129 ethnicity.

130 The goal will be to include at least 50 participants  $<25$  years of age and at least 50 participants  
131  $>65$  years of age.

132 **2.1.1 Informed Consent and Authorization Procedures**

133 Individuals who indicate that they are interested will be directed to a website with information  
134 about the study. Interested individuals will be able to communicate with study staff who can  
135 answer questions about the study as part of the informed consent process. Individuals who want  
136 to participate in the study will sign the Institutional Review Board (IRB) approved electronic  
137 consent form. As part of the informed consent process, each participant will be asked to sign an  
138 authorization for release of personal information. Participants will be asked to sign an addendum  

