212 Other sensors that become FDA approved during the course of the study may be included as an  
213 option for participants. If additional sensors are included, the participants will be given  
214 information about CGM system options and will review the CGM systems with a study team  
215 member. A recommendation may be provided for one of the systems based on discussion with  
216 the participant, or there may be an indication that there is no specific recommendation.  
217 Participants will be able to select the CGM system that they prefer, regardless of  
218 recommendation. After a CGM system is selected, the participant may be asked why that system  
219 was selected.

220 **2.7 Blinded CGM**

221 Non-CGM users will use a blinded CGM device for a single sensor wear period (usually at least  
222 10 days) prior to CGM initiation. Current CGM users will be asked to use a blinded CGM device  
223 for a single sensor wear period if their current CGM data cannot be successfully shared to  
224 confirm eligibility. Study supplies required for blinded CGM data collection will be sent to the  
225 participant by mail. An Android phone may be provided which is used as a receiver to collect  
226 data from the blinded Dexcom G6 Pro. Current non-Dexcom CGM users, including pump users  
227 with integrated CGM should continue to use their personal CGM for glucose management.

228 A virtual clinic team member will be available to answer questions about blinded CGM use. The  
229 participants will not be able to see the glucose values and will be expected to follow their normal  
230 diabetes management practice during this blinded CGM use period. The goal will be to obtain  
231 ten days of blinded data. Participants may be asked to use a blinded CGM for an additional  
232 sensor wear period if enough CGM data are not available to establish baseline comparator data.  
233 Participants will be dropped from the study if blinded data cannot be obtained. Participants who  
234 have a serious skin reaction to the sensor during blinded CGM wear that precludes continued use  
235 of a sensor will be dropped. If additional FDA-approved CGM options are available for use in  
236 this study, the participant may be offered the opportunity to try the other CGM system; in this  
237 case blinded data collection would be repeated with another system.

238 **2.8 Psychosocial Screening Questionnaires**

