The goal for the study is to include at least 300 participants who initiate CGM. This is a convenience sample and not based on statistical principles.

5 Outcome Measures

The following quantitative study outcome measures will be tabulated by diabetes type using summary statistics appropriate to the distribution:

- HbA1c
- Percentage of time using the CGM
- Hours of CGM use
- Mean of sensor glucose levels
- Percentage of time spent with sensor glucose levels <54 and <70 mg/dL
- Percentage of time spent with sensor glucose levels >180 and >250 mg/dL
- Percentage of time spent with sensor glucose levels in the target range (70-180 mg/dL)
- Glycemic variability measured by the coefficient of variation
- Total daily insulin (units/kg)
- Total daily basal insulin (units/kg)
- Total daily bolus insulin (units/kg)
- Patient Health Questionnaire-8
- Diabetes Distress Scale Management Distress Subscale
- Hypoglycemia Fear Survey Worry Subscale
- CDC Healthy Days
- Hypoglycemia Confidence Survey
- Diabetes Technology Attitudes Survey
- Glucose Monitoring Satisfaction Survey
 - Openness Subscale
 - Emotional Burden Subscale
 - Behavioral Burden Subscale
 - Trust Subscale
- Sleep Quality Scale
- Benefits and Barriers of CGM Survey
- Percentage of CGM discontinuations
- CGM Discontinuation Survey (only administered to subjects who discontinue CGM)
- Positive screen for mental health

41 ○ Positive screen triggered by Patient Health Questionnaire-8
 42 ○ Positive screen triggered by Diabetes Distress Scale
 43 ○ Positive screen triggered by Hypoglycemic Fear Survey Worry Scale
 44 • Behavioral health service utilization
 45 • Behavioral health metrics
 46 • Cost of care over time
 47 • Service utilization such as hospitalizations, ER visits, prescriptions filled

48
 49 CGM, HbA1c, and insulin outcomes will be evaluated at baseline and 13, 26, 39, and 52 weeks.
 50 CGM and insulin outcomes will also be evaluated over the first 26 weeks and last 26 weeks.
 51 Questionnaires will be evaluated at all time points they are collected.

52 **6 Description of Statistical Methods**

53 **6.1 Analysis Cohorts**

- 54 • All subjects enrolled in the study who initiate the CGM and have at least 168 hours of
 55 CGM data will be included in the tabulations of demographics and the glycemic
 56 outcome measures listed in Section 5
- 57 • CGM use assessment will include all subjects who stayed in the study at least one week
 58 following CGM initiation.

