- 59 • HbA1c, questionnaires, insulin, and other analyses will include all subjects with any
 60 amount of corresponding data following CGM initiation.
- 61 • The tabulations of the safety outcomes will include all participants who enrolled,
 62 regardless of how much data is available.

63 **7 Analysis of Study Endpoints**

64 **7.1 Calculation of CGM Metrics**

65 **7.1.1 Calculation of 13 Week CGM Metrics**

66 All CGM metrics listed in Section 5 will be calculated on a 13-week period for each subject
 67 level. The windows for the 13-week periods are defined as follows:

Time Point	Window
1-13 Weeks	0 to 91 days after the CGM initiation date
14-26 Weeks	92 to 183 days after the CGM initiation date
27-39 Weeks	184 to 274 days after the CGM initiation date
40-52 Weeks	275 to 365 days after the CGM initiation date

68
 69 For each 13-week period, CGM metrics will be calculated by pooling all CGM readings
 70 occurring from 12:00 AM on the first day of the 13-week period up until 11:59PM on the last
 71 day of the 13-week period. For the first 13-week period, the first CGM reading will be the start
 72 datetime of the period. If a participant discontinues CGM prior to the last day of the 13-week
 73 period, then CGM data will include readings up to the last CGM reading on the discontinuation
 74 date. Calibrations will be excluded from all these calculations. CGM metrics for 13-week periods
 75 with less than 168 hours of CGM data will be set to missing.

76 Baseline CGM metrics will be calculated by pooling all blinded CGM readings up to 90 days
77 prior to the date of CGM initiation for each subject. Baseline CGM metrics with less than 72
78 hours of CGM data will be set to missing.

79 The amount of time using the CGM will be calculated as the number of CGM values multiplied
80 by the expected CGM measurement frequency (i.e., 5min in general), with the exception that
81 there can only be one value within the CGM measurement frequency. Percentage of time CGM
82 is used will be calculated as the amount of time using the CGM divided by the total possible time
83 the participant could have used the CGM during the same period. Note that this denominator
84 includes sensor warm-up periods with no CGM values, so this metric will serve as a conservative
85 estimate of CGM use.

86 **7.1.2 Calculation of 4 Week CGM Metrics**

87 All CGM metrics listed in Section 5 also will be calculated on a 4-week interval for each subject.

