7.4 Statistical Methods

For all outcomes, summary statistics appropriate to the distribution will be tabulated on a subject level overall and within the subgroups defined in Section 12. For the CGM metrics, summary statistics appropriate to the distribution also will be tabulated for each 4-week interval and for the first and last 26 weeks of the study. For the questionnaires, summary statistics will be reported for the mean scores in addition to the individual responses for each question.

For all outcomes, a linear mixed model with a random subject effect will be used to test whether the mean change from baseline significantly differs from zero. These models will be fit for each of the subject level CGM metrics and HbA1c at 13, 26, 39, and 52 weeks. They also will be fit for the questionnaires at 26 and 52 weeks. If values are skewed, then winsorization will be utilized. Point estimates and 95% confidence intervals for change in glycemic outcomes will be reported.

For the three mental health screening questionnaires, only summary statistics will be tabulated. The three mental health screening questionnaires falling under this umbrella are the Patient

187 Health Questionnaire-8, the Diabetes Distress Scale (Management Distress Subscale), and the
188 Fear of Hypoglycemia Survey (Worry Subscale).

189 **7.5 Analyses Windows**

190 For HbA1c, only measurements occurring within ± 45 days of the target measurement date at a
191 given time point will be included in the tabulation of summary statistics. The windows for
192 glycemic metrics were defined above in Section 7.1.

193 **7.6 Sensitivity Analyses**

194 For CGM and HbA1c outcomes, a complete-case analysis restricting to non-missing outcomes
195 will also be assessed. A paired t-test (for normally distributed outcomes) or a Wilcoxon signed
196 rank test (for skewed outcomes) will be used.

197 **8 Safety Analyses**

198 All adverse events that occur on or after the date of enrollment will be listed in a table.

199 For events occurring on or after the date of CGM initiation, the reported safety outcomes include
200 diabetic ketoacidosis (DKA), severe hypoglycemia (SH), hospitalization, and emergency room
201 visits. The following statistics will be tabulated for each safety outcome:

- 202 • Total number of events
- 203 • Number and proportion of subjects with an event (discretized into bins)
- 204 • Incidence rate per 100 person years

205

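### For time <54 mg/dL, the signed-rank test in SAP 7.6 compares about 10 baseline days with about 91 follow-up days and can report a rise when nothing has changed; winsorizing without stated limits adds to the problem

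*SAP*

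**What the plan says.** SAP 5 lists "Percentage of time spent with sensor glucose levels <54 and <70 mg/dL" among the outcomes, and SAP 3 tests change from baseline against zero, by diabetes type.

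The two sides of that change come from windows of different length:
- **Baseline.** Protocol 2.7 sets a goal of "ten days of blinded data" from a single sensor wear, with a repeat wear possible. SAP 7.1.1 states: "Baseline CGM metrics will be calculated by pooling all blinded CGM readings up to 90 days" before CGM initiation. "Baseline CGM metrics with less than 72" hours of data are set to missing, so 72 hours is enough.
- **Follow-up.** SAP 7.1.1 states: "For each 13-week period, CGM metrics will be calculated by pooling all CGM readings" in that period. The first period runs from day 0 to day 91.

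For skew, SAP 7.4 provides: "If values are skewed, then winsorization will be" utilized. It does not say at what percentiles, whether limits are set per visit or pooled, or whether visit values or changes are capped. Protocol 6.5 gives no limits either and also allows a transformation. SAP 7.6 adds a complete-case analysis in which a Wilcoxon signed "rank test (for skewed outcomes) will be used". Neither document addresses the unequal windows.

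**The concern.** The signed-rank test assumes that, under no change, differences are symmetric about zero. A short window of a rare, episodic quantity breaks that symmetry: many participants read zero or close to it, and a few read very high. The mean of the difference is still zero, but its median is not. The test reads the asymmetry as a rise in hypoglycemia. Capping does something similar, because it trims the long upper tail of the noisier baseline more than that of follow-up.

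Two results are at stake. Window length alone could produce a reported rise in time <54 mg/dL, or a real fall could appear unconfirmed. The subject-level summaries in SAP 7.4 would not expose this, because a median change carries the same bias.

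**Working it through.** The plan states no error rate or power for these tests (the 300 is a convenience sample), so there is no figure to reproduce.

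**Inputs from the documents.** Baseline 10 days, minimum 72 hours; follow-up 91 days; two-sided alternative (SAP 3). N = 200 is 300 minus the type 2 limit in Protocol 2.1 ("The goal will be to limit T2D enrollment to no more than 100").

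**Assumed inputs.** Alpha 5%. True time <54 is lognormal across people with median 0.3% and log SD 1.11. The share above 1% is then P(Z > ln(1/0.3)/1.11) = P(Z > 1.08) = 14%. Episodes arrive at random with exponential lengths averaging D = 30 or 60 minutes. Runs were made without and with between-period fluctuation of log SD 0.3.

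**Step 1: one person at the median, p = 0.3%.** Expected episodes in d days: λ = 14.4 × p × d / D.

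| Window | λ, D = 30 | λ, D = 60 | P(reads exactly 0) = exp(−λ) |
|---|---|---|---|
| 3 days | 0.43 | 0.22 | 65%, 81% |
| 10 days | 1.44 | 0.72 | 24%, 49% |
| 91 days | 13.1 | 6.6 | about 0% |

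The expected reading is 0.3% in every window. The chance of reading below it in 10 days is the sum over k of P(k episodes) × P(Gamma(k) < λ):
- D = 30: 0.24 + 0.26 + 0.10 + 0.02 = 62%.
- D = 60: 0.49 + 0.18 + 0.02 = 69%.

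So the error has mean zero and a median below zero.

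**Step 2: 200 people, no true change, 10 against 91 days (simulation).** About 62-65% read lower at baseline than at follow-up, 30-36% read higher, and 30-48% read exactly zero at baseline. The signed-rank statistic is the sum of the ranks of the positive differences, compared with n(n+1)/4. It is pushed upward.

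| Test | Wrong results, no true change |
|---|---|
| Signed-rank, 10 vs 91 days | rise in about 37-69%, fall in about 0% |
| Signed-rank, equal windows | 5-6% in total |
| Winsorized, pooled 1/99 | rise in about 5% |
| Winsorized, pooled 5/95 | rise in 9-18% |
| Winsorized, pooled 10/90 | rise in 22-46% |
| Unwinsorized mean, paired test | about 5-6% in total |

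The winsorized rows are paired tests. The equal-window row isolates window length as the cause.

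**Step 3: other inputs, signed-rank false rise.** 14-day baseline: 25-47%. One in five people with a 90-day baseline: 31-62%. N = 100: 22-39%. Time <70 (median 2%, episodes of 45-90 minutes): 9-18%. A different generator, using daily values and drift: 17-44%.

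**Step 4: a true fall in everyone.** Detection by the signed-rank test:

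| True fall | 10 vs 91 days | Equal windows |
|---|---|---|
| 20% | 0-18% | 36-62% |
| 30% | 6-73% | 67-94% |

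With a 20% fall, the test on unequal windows still reports a false rise in 0-9%.

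**Step 5: the unwinsorized mean in the planned model.** Within-person noise variance is proportional to 1/d, so baseline carries 91/10 = 9.1 times the variance of a 13-week period. A random-intercept model over five visits with one residual variance averages these: (9.1 + 4 × 1)/5 = 2.62. It uses 2 × 2.62 = 5.24 where the true variance of the change is proportional to 9.1 + 1 = 10.1. The standard error is too small by √(5.24/10.1) = 0.72, and P(|Z| > 1.96 × 0.72) = 16%. Simulation gives about 11-17%, in both directions. The estimate itself is unbiased.

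**The case against.** The best case for leaving the plan alone has four parts.

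1. SAP 1 calls all analyses exploratory, SAP 3 names no primary outcome, and SAP 7.6 is a complete-case check on missing data. This stands and limits the severity. It does not make the test informative: a check that leans one way cannot support or contradict the main result.

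2. Every rate rests on an assumed frequency, length and clustering of hypoglycemia. This also stands. The direction follows from the window lengths; the size does not. A longer baseline, from a repeat wear or from shared data of current CGM users, shrinks the error without removing it.

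3. Winsorizing is ordinary practice and does little harm at 1/99. True, but the plan does not commit to 1/99. At 10/90, setting limits per visit gives 18-25% wrong results in total, while pooled limits give false rises in 22-46%, so the unstated details matter.

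4. A large effect would show anyway: with a 50% fall, the signed-rank test detects it in 76-100%. This is fair. The problem lies with small or absent changes.

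A reader might also infer that the unwinsorized mean is safe under any planned analysis. The documents do not support that: SAP 7.4 does not state the visit structure or residual variances, and one common variance over five visits is wrong too often (step 5).

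**Conclusion.** The point holds, with modest severity. For time <54 mg/dL, and less so for <70 mg/dL, the signed-rank test as planned does not test for a change in hypoglycemia alone; it also responds to the difference in window length. Under the assumed inputs it gives a false rise in about 37-69% of datasets and often misses moderate real falls. Winsorizing has the same bias, growing with the cap, and is close to harmless at 1/99. The unwinsorized mean change is unbiased; its test is sound if paired or if the model lets baseline be noisier.

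A reader might infer that the main hypoglycemia analysis is invalid, or that a false rise is near certain because 72 hours of baseline is allowed (96-100% in simulation). Neither is supported. The winsorizing limits are unknown, and the 72-hour figure gives everyone the minimum, although ten days is the goal and repeat wear is planned.

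**What to change.** Change two sections of the SAP, for time <54 and <70 mg/dL only.

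- **SAP 7.6.** Run the signed-rank test on a follow-up window holding the same hours of data as that participant's own baseline, with its position fixed in advance (for example, the last such hours of each 13-week period). Say that the result describes that shorter window and not the full 13 weeks.
- **SAP 7.4.** Report the unwinsorized mean change with a 95% CI from the planned mixed model, with visit-specific residual variances or a robust standard error. This keeps the direct-likelihood handling of missing data in SAP 7.3, which a paired interval would give up. It was not simulated, but with complete data the estimate is the mean paired change, and a subject-level robust standard error is essentially the paired one. If a winsorized estimate is also shown, set the limits in advance at the 1st and 99th percentiles of values pooled over visits.

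The cost is a few sentences and no new data; the 13-week metrics and tables stay as they are. There are two downsides. The unwinsorized mean is more sensitive to a few extreme participants. The matched-window test uses fewer follow-up days, although under these inputs it still detects true falls more often than the test as planned.

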	
 
Planned relocation to a state other than current state of residence during the study if virtual clinic is not licensed in the new state. Individuals working routinely in a state other than current state of residence in the next six months are also ineligible if the virtual clinic is not licensed in that state.
 

Sample Size	The recruitment target is 300 initiating CGM.
Outcomes	
Efficacy Outcomes: CGM use; CGM metrics for hypoglycemia (<54 and <70 mg/dL), hyperglycemia (>180 and >250 mg/dL), time in range (70-180 mg/dL), mean glucose, and glycemic variability (coefficient of variation); HbA1c; participant- reported outcomes including psychosocial and diabetes treatment satisfaction questionnaires
 
Safety Outcomes: Severe hypoglycemia, diabetic ketoacidosis, hospitalizations, and emergency room visits

Participant Duration	Study participation will be up to 12 months.

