Protocol Overview/Synopsis	
Patient Population Adults ≥ 18 years with type 1 diabetes or type 2 diabetes using insulin therapy will be enrolled. Although the primary focus of the study is to enroll non-CGM users, CGM users whose glycemic control is suboptimal can be enrolled. Potential participants may be recruited through insurance providers, primary care networks, or health care providers.
 
Baseline Data Collection Baseline data collected will include demographics, height and weight, socioeconomic status, diabetes history, knowledge of and experience with diabetes devices, medical history and medications, and health-related physical activity. Questionnaires will collect information related to hypoglycemia awareness, treatment satisfaction, and psychosocial issues. Participant contact information will be collected. Contact information for the participant's diabetes healthcare provider will also be collected.
 
HbA1c Participant will receive fingerstick HbA1c kits that will be sent to a central lab for measurement after enrollment and at 13 weeks, 26 weeks, 39 weeks, and 52 weeks.
 
Contact between Study Team and Participant Each participant will be assigned to work with virtual clinic team members. Mental health service support options for diabetes-related mental health issues will be discussed as needed.
 
Virtual clinic team members will check in with participants during the initial six months of study follow up to review CGM data and recommendations related to diabetes management. Participants who continue in the optional extended follow-up phase after the first six months can contact the virtual clinic as needed.
 
CGM Use Participants who do not currently use a CGM will use a blinded CGM device for a single sensor wear period prior to CGM initiation. Participants may be asked to use a blinded CGM for an additional sensor wear period(s) if enough CGM data are not available to establish a baseline that can be used as baseline comparator data. Current CGM users will be asked to share their CGM data to confirm that they meet study eligibility criteria and to establish a baseline that can be used as baseline comparator data. Virtual training will include CGM set up, sensor insertion, alerts and alarms, uploading data, and visualizing data.
 
Changes in Insulin Dosing

JAEB CENTER FOR HEALTH RESEARCH

PARTICIPANT AREA	DESCRIPTION

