139 consent for follow up after the first 6 months if they plan to continue use of CGM.

140 **2.2 Participant Inclusion Criteria**

141 Individuals must meet all the following inclusion criteria in order to be eligible to participate in  
142 the study:

- 143 1. Age  $\geq 18$  years old
- 144 2. Diagnosis of type 1 diabetes or type 2 diabetes and using insulin therapy (at least 3 injections  
145 of insulin per day or insulin pump that is compatible with Tidepool software)  
*146 Multiple daily injection (MDI) users must be willing to enter insulin dosing information  
147 through an app*
- 148 3. See a healthcare provider at least once a year
- 149 4. Resident of United States and plan to reside in the U.S. for the duration of the study  
*150 This requirement is due to virtual clinic license requirements and U.S. use restrictions for  
151 some study software and devices. Not all U.S. states may be eligible for inclusion due to  
152 virtual clinic license status.*

153 5. Use either an Android or iOS smartphone that is compatible with app requirements that are  
154 needed for the study  
155 6. Access to a compatible computer with internet  
156 7. Understand written and spoken English  
157 8. Willing and able to follow the study procedures as instructed

158 **2.3 Participant Exclusion Criteria**

159 Individuals meeting any of the following exclusion criteria at baseline will be excluded from  
160 study participation:

161 1. Current use of a closed loop system where an insulin pump and CGM share information and  
162 insulin dose is automatically adjusted based on glucose reading  
163 2. Current CGM use where Time in Range is  $\geq 60.0\%$  or Time  $< 54\%$  is  $\leq 1.0\%$ .  
164 3. Current use of any off-label glucose-lowering medications for diabetes type (Example: T1D  
165 use of non-insulin, anti-diabetic medications including SGLT2 inhibitors)  
166 *Use of such medications during the study will also be prohibited.*  
167 4. Females who are pregnant, intending to become pregnant, or breastfeeding during the study  
168 5. Current renal dialysis or plan to begin renal dialysis during the study  
169 6. Active cancer treatment  
170 7. Extreme visual or hearing impairment that would impair ability to use real-time CGM  
171 8. Known adhesive allergy/prior skin reaction or skin reaction identified during the blinded  
172 CGM use phase that would preclude continued CGM use  

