### 428      **6.3 Outcome Measures**

429      The following outcome measures will be stratified by type of diabetes.

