206 The number of person-years for the incidence rate calculations will be inclusively defined as the
207 number of person-years in between the CGM initiation date and the last day of study follow-up
208 (completion date, withdrawal date, etc.).

209 **9 Adherence and Retention Analyses**

210 **9.1 Protocol Adherence**

211 The number of and reasons for participant contacts with the virtual clinic will be reported in a
212 table to assess protocol adherence for the study.

213 **10 Baseline Descriptive Statistics**

214 Baseline demographic and clinical characteristics of the cohort of all subjects who initiate the
215 CGM and were included in the glycemic analyses will be summarized in a table. Use of
216 medications and non-insulin therapy will also be reported. For continuous variables, summary
217 statistics appropriate to the distribution will be given. For discrete variables, number and
218 percentage will be reported for each category. Summary statistics for demographics and clinical
219 characteristics will be presented overall, by diabetes type, by insulin modality, by whether the
220 participant was seeing an endocrinologist or a primary care provider at baseline, by baseline
221 HbA1c groups ($<7.5\%$, 7.5% to $<9.0\%$, and $\geq 9.0\%$), and by age (<25 , $25\text{-}65$, and >65 years). Cut
222 points for age and baseline HbA1c may be reassessed after data are collected.

223 **11 Planned Interim Analyses**

224 No formal interim analyses or stopping guidelines are planned for this study. Data will be
225 monitored on an ongoing basis including:

- 226 • Status of enrolled participants
- 227 • Recruitment rates by month and by site
- 228 • Baseline demographic and clinical characteristics
- 229 • Dropped participants and reasons for discontinuing
- 230 • Reportable adverse events

231 **12 Subgroup Analyses**

232 Subgroup analyses for % of time using the CGM, % time in range, % time >180 mg/dL, % time
233 <70 mg/dL, and HbA1c will be performed based on the following factors:

- 234 • Baseline HbA1c (categorized as <7.5%, 7.5% to <9.0%, and ≥9.0%)
- 235 • Insulin modality
- 236 • Age (categorized as <25, 25-65, and >65)
- 237 • Type of healthcare provider (endocrinologist or primary care provider)
- 238 • Diabetes Duration (categorized as <5, 5-<10, 10-<20, ≥20)
- 239 • Race/Ethnicity
- 240 • Household income (categorized as <\$50,000, \$50,000-<\$100,000, and ≥\$100,000)

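### The SAP was written for people who do not use CGM, but the protocol admits current CGM users without a numeric limit, and no analysis separates them from people starting CGM

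*SAP*

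**What the plan says.** **Population in the protocol.** The Protocol Summary states "Although the primary focus of the study is to enroll non-CGM users" but adds that "CGM users whose glycemic control is suboptimal can be enrolled"; Protocol 2.1 repeats this. Exclusion 2 in Protocol 2.3 ("Current CGM use where Time in Range is" at least 60.0%, or time below 54 at most 1.0%) filters who may enter but does not limit how many. Protocol 2.1 sets numeric goals for other features: "The goal will be to limit T2D enrollment to no more than 100", at least 225 with no endocrinologist visit in six months, and at least 50 in each of the youngest and oldest age groups. It sets none for current CGM users. The Protocol Summary gives the overall figure as "The recruitment target is 300 initiating CGM".

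**Population in the SAP.** The SAP title page names Protocol 2.0 as its basis. SAP Table 1 excludes real-time CGM use in the last 12 months and describes the population as people who do not use CGM.

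**Cohorts and breakdowns.** SAP 6.1 takes everyone who initiates CGM, subject only to minimum data or time in study. Protocol 6.3 says "The following outcome measures will be stratified by type of diabetes", and SAP 3 agrees. SAP 12 begins "Subgroup analyses for % of time using the CGM, % time in range, % time >180 mg/dL, % time" and lists baseline HbA1c, insulin modality, age, provider type, diabetes duration, race/ethnicity and income; discontinuation is tabulated by the same factors. SAP 10 breaks the baseline table down by a shorter list. Protocol 6.6 names HbA1c group, insulin modality, age and provider, and leaves other characteristics to the SAP. Baseline CGM use appears in none of these.

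**Baseline CGM data.** SAP 7.1.1 builds baseline from blinded readings within 90 days before initiation. The protocol's schedule footnote and section 2.7 ask current users for blinded wear only if their own data cannot be shared.

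**The concern.** The study title asks about remote initiation of CGM. In a non-user, change from baseline reflects starting CGM together with clinic support. In a current user it reflects clinic support and, for some, a change of sensor. Protocol 1.1 gives current users a separate rationale: help in understanding data they already have. One mean over both groups answers neither question cleanly.

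Uptake has the same difficulty. Continued use and discontinuation mean something different in a person who already wore a sensor at entry, and persistence in that group is likely to be higher. A reader of the report could not tell how far a good uptake figure came from people who had already adopted CGM, because the mix is uncontrolled and no planned table displays it.

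**Working it through.** There is no sample-size figure to reproduce: both documents call the 300 a convenience sample. The check is which outcomes are mixed and how, followed by an illustration.

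**Step 1: trace a current user who shares data through the SAP**

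| Outcome | SAP rule | Result |
|---|---|---|
| HbA1c | 6.1: any data after initiation; baseline sample taken from all | Fully pooled |
| CGM use | 6.1: at least one week in study | Fully pooled |
| Discontinuation | 5 and 12: no split by baseline CGM use | Fully pooled |
| Change in CGM metrics, mixed model | 7.1.1: blinded baseline only; 7.3: no imputation | Baseline missing; follow-up values only |
| Change in CGM metrics, paired test | 7.6: complete cases | Drops out |

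The mixed-model row takes baseline as one of the repeated values, the natural reading of the direct-likelihood approach in SAP 7.3. If change scores were modelled instead, these participants would drop out there too. On the first reading, baseline is missing by design in one group. Group is not in the model, so the baseline mean comes from non-users (plus any current users who wore a blinded sensor), while the follow-up means include everyone.

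**Step 2: illustration for HbA1c, which is fully pooled**

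Let q be the share of current users among the 300 and r their change as a fraction of the non-user change. Both are assumptions; the documents give neither.

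Pooled change / non-user change = (1 − q) + q × r

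| q | r = 0.5 | r = 0 |
|---|---|---|
| 5% | 0.975 | 0.95 |
| 10% | 0.95 | 0.90 |
| 20% | 0.90 | 0.80 |
| 30% | 0.85 | 0.70 |

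If r exceeds 1, the ratio exceeds 1 and pooling overstates the non-user change. That is possible: the Protocol Summary uses current users' shared data both to confirm eligibility and to set their baseline, and selection on poor readings invites regression to the mean.

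**Step 3: illustration for uptake**

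Assume 80% continued use in non-users and 100% in current users. Pooled use = (1 − q) × 80% + q × 100%, which is 82%, 84% and 86% at q = 10%, 20% and 30%.

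Assume discontinuation of 15% and 3%. Pooled discontinuation = (1 − q) × 15% + q × 3%, which is 13.8% at q = 10% and 11.4% at q = 30%.

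**Step 4: precision after a split**

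95% half-width for a mean change = 1.96 × SD / √n, where SD is that of the change. With all 300 it is 1.96/√300 = 0.113 SD.

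| q | n non-users | Half-width | n current users | Half-width |
|---|---|---|---|---|
| 5% | 285 | 0.116 SD | 15 | 0.51 SD |
| 10% | 270 | 0.119 SD | 30 | 0.36 SD |
| 20% | 240 | 0.127 SD | 60 | 0.25 SD |
| 30% | 210 | 0.135 SD | 90 | 0.21 SD |

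The smallest difference between groups detectable with 80% power at two-sided 0.05 is (1.96 + 0.84) × SD × √(1/n₀ + 1/n₁): 0.54, 0.40 and 0.35 SD at q = 10%, 20% and 30%. The non-user estimate loses little precision; a formal comparison of the groups would be weak.

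**The case against.** The strongest reply is that the SAP never chose to pool. Its own eligibility text leaves no current users to separate, so the fault lies in alignment with the protocol and not in SAP 12. This stands as a diagnosis, and an extra line in SAP 12 alone would leave the population text and the baseline rule in conflict with the protocol. It does not remove the consequence: applied to the protocol's population, the SAP gives mixed results.

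A second reply is that few current users may enter. As written, exclusion 2 removes a user who meets either limb, closed-loop users are also excluded, and non-users are the stated focus. This stands too, and is why no magnitude can be asserted.

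A third is that every analysis is exploratory, there is no primary outcome, further analyses are allowed, and the table shells are in a separate document. A later split is therefore possible. It is weaker than a planned one, and the SAP text is where the factors are defined.

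A fourth is that the stated objective concerns the clinic model, which an overall estimate addresses, and that the recruitment goal in Protocol 2.1 counts people starting training with the clinic, which a current user can do. That justifies keeping an overall result. It does not make that result an estimate of initiation.

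A reader might go further and infer that pooling dilutes the time-in-range change by a simple weighted average. The documents do not support this: data-sharing current users have no SAP baseline, so that formula does not describe the planned analysis. A reader might also infer that current users receive no CGM component. Protocol 2.6 has participants use the Dexcom G6, and Protocol 1.1 contrasts its alerts with flash systems read by scanning, so some would gain a device feature.

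**Conclusion.** The point holds as a mismatch between SAP and protocol with a definite analytic consequence. HbA1c, CGM use and discontinuation would combine people starting CGM with people already using it, and no planned breakdown shows the mix. Change in CGM metrics has a different defect: an undefined baseline for current users who share data.

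The size and direction of the net bias are not determinable from the documents. The figures for 5% to 30% current users show scale only and rest entirely on assumed shares and effects. Lower glycemic change in the pooled group is plausible, but regression to the mean could push the other way. Higher uptake in current users is likely, not established. It would also be wrong to read the current-user change as isolating the effect of clinic support: there is no control group, and the readings that confirm eligibility also form the baseline.

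The SAP should be corrected before analysis. With all analyses exploratory and current users identified at screening, the correction is straightforward.

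**What to change.** - Align the population and eligibility text in SAP Table 1 with the protocol.
- In SAP 7.1.1, define the baseline CGM source for current users as their shared data, flagged as unblinded.
- Add baseline CGM use (non-user or current user) to the breakdowns in SAP 10 and SAP 12, including discontinuation.
- Base statements on CGM initiation and uptake on non-users. An overall result can stay alongside.
- Report how many of those initiating are current users. Show their results separately and descriptively, with a regression-to-the-mean caveat and without calling them an effect of clinic support.
- Do not cross baseline CGM use with diabetes type where cells are small. At an assumed 10% in each type, at most 100 T2D participants would include about 10 current users, with a half-width of 1.96/√10 = 0.62 SD.

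No new data are needed: Protocol 2.4 identifies current users at screening, and Protocol 2.5 collects prior CGM experience. The cost is SAP wording, extra table columns and a slightly wider interval for the initiation estimate (0.119 to 0.135 SD against 0.113 SD if 10% to 30% are current users). Results for current users will be imprecise.
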